### b. Secondary Outcomes

Secondary outcomes for the trial include the following outcomes from the PROMIS – Pediatric and Parent Proxy Instruments. The PROMIS instruments used are Children's physical activity (PA), sleep, stress, depression, and anxiety. Parents' PA, sleep, stress, depression and anxiety. The final score is represented by the T-score, a standardized score with a mean of 50 and a standard deviation (SD) of 10.

The outcome measures will be collected at baseline, and months 5 and 7 surveys.

## 8. Primary exposure definition

In keeping with intention-to-treat analysis principles, the primary exposure of interest is randomization group as determined by the appropriate random allocation list(s). Even if a participant is mistakenly given the incorrect group assignment in implementing the study, they will be analyzed in the group to which they were randomly assigned according to the appropriate random allocation list. Using the random allocation assignment will avoid any actual or appearance of potential selection bias in the comparison groups, but could bias trial results towards the null when such errors are made. All efforts should be made to avoid such errors.

## 9. Interim analysis plan

For this study there were no interim analysis.

## 10. Multiple testing

We will adjust for multiple testing by controlling FDR.

## 11. Missing Data

After enrollment data collection, some missing demographic information was included in post survey one. We used the later data to fill in missing data over multiple time points. We gathered as much information as possible by engaging in multiple follow-up attempts. Incentives were used to have as few participants drop out as possible and to keep participants engaged.

For other missing data at the end, we will inspect missing data mechanisms and the amount of missing data. We will conduct an additional sensitivity analysis with multiple imputations using multivariate imputation with chained equations (MICE) approach. We will report the amount of missing data and apply appropriate methods to account for the missing data.

## 12. Planned Statistical Analyses

### a. CONSORT diagram

Screening and enrollment into the study will be shown in a CONSORT-style diagram, with summary of reasons for ineligibility or non-enrollment; randomization assignment into the two groups, and retention to the 5-month and 7-month outcome assessments.

### b. Baseline Demographics

Baseline characteristics of enrolled participants will be summarized by randomization group, and overall, in a table. It is expected that children in both allocated groups will, on average, be similar, given the randomization procedure.

### c. Efficacy Analyses Overview

Post survey 1 outcome analyses will be conducted after all participants have been contacted and the survey is closed with missing responses marked as loss to follow-up but before the collection of the second round of surveys began. Post survey 2 outcome analysis will be conducted after all participants have been contacted and the survey is closed.

All efficacy analyses will be performed using the intention-to-treat method in the sense that randomly assigned group will be our exposure regardless of adherence to POC testing offered. In addition, for our combined ART care outcome, we have designed the outcome to minimize missing data for our primary comparisons.

#### i. Descriptive Analyses:

Positive COVID test results from the school district testing program will be summarized by counts by randomization group. Vaccine status and covid testing results will be summarized by counts and percentages by randomization group. Continuous variables by mean, standard

deviation(SD) and median (IQR) by randomization group. Secondary outcomes will be summarized and compared using Chi-squared tests

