## 3. Study Design

ROSSEY study is a cluster randomized controlled trial to test COVID-19 risk communication intervention with 900 participants from 14 elementary schools in the Yakima School District during

the 2022-2023 school year. Schools are randomized 1:1 (matched by school size and English language learners) to either intervention or control group. Students and parents randomized to the intervention group receive the COVID-19 risk communication intervention. Students and parents randomized to the control group receive the same risk communication intervention at the end of the study as a delayed intervention.

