### Study Timeline

## 4. Sample size and power

**For month 5 outcome.** We will enroll 900 elementary school students from 14 schools in the Yakima School District during the 2022-2023 school year. The sample size of 7 schools per study arm and an average of 50 students per school will provide 90% power to detect a difference of at least 4 hours per week ( $SD=8.0$ ) of in-person school attendance between the intervention and control groups, while assuming intra-cluster correlation (ICC) of 0.05 and type I error rate of 0.05. The estimated sample size of 14 schools with 900 students provides 80% power to detect a difference of 20% or more in COVID-19 vaccination rates between the two study arms, assuming ICC of 0.05 and type I error rate of 0.05.

Minimum detectable difference in hours per week between intervention arms in proposed cluster RCT assuming enrollment of 15 students per classroom, 80% power and two-sided type I error rate of 0.05.					
		Two Arm			
	Number of clusters per arm	30		40	
	ICC	.01	.10	.01	.10
Standard Deviation	5.0	1.0	1.5	.87	1.3
	7.5	1.5	2.2	1.3	1.9

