## 6. Presentation of comparative analyses

For each of the continuous outcomes (including the primary outcome), the mean and standard deviation for each allocated group will be presented, together with the mean between-group difference, 95% confidence interval for the difference and p value. For binary outcomes, the percentage and frequency of children in the outcome category of interest (e.g. percentage vaccinated) will be presented for each allocated group, along with the odds ratio for the intervention effect, 95% confidence interval for the odds ratio and p value.

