## iii. Secondary outcomes

The secondary outcomes for the trial include measures from the PROMIS – Pediatric and Parent Proxy Instruments. The PROMIS instruments used are Children's PA, sleep, stress, depression, and anxiety; Parents' PA, sleep, stress, depression and anxiety. We will compare the scores for each of the items between the control and intervention arms at months 5 and 7. We will use a linear mixed effects regression models to determine whether between-arm differences were statistically significant.

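### The SAP's descriptive section assigns Chi-squared tests to secondary outcomes that are continuous T-scores from school-randomised children, in conflict with its own linear mixed model

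*SAP*

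**What the plan says.** Four places in the SAP bear on how secondary outcomes are compared.

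- **Section 12c.i (Descriptive Analyses):** "Secondary outcomes will be summarized and compared using Chi-squared tests". It gives no qualifier, categories or term for school. The same paragraph summarises continuous variables by mean, SD, median and IQR.
- **Section 7b (Secondary Outcomes):** the outcomes are PROMIS measures of physical activity, sleep, stress, depression and anxiety, each for child and parent. On the scale: "The final score is represented by the T-score, a standardized score with a mean of 50 and a standard deviation (SD) of 10".
- **Section 12c.iii (Secondary outcomes):** the same scores are compared between arms at months 5 and 7. "We will use a linear mixed effects regression models to determine whether between-arm differences were statistically significant". No random effect is named.
- **Section 6 (Presentation of comparative analyses):** for continuous outcomes, "the mean and standard deviation for each allocated group will be presented, together with the mean between-group difference, 95% confidence interval for the difference", with a p value.

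On design, SAP section 3 says: "Schools are randomized 1:1 (matched by school size and English language learners) to either intervention or control group".

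The Protocol differs on one item. Its Aim 2 text in the Study Design section lists COVID-19 vaccination, a binary outcome, among the secondary outcomes. SAP section 7a makes vaccination co-primary.

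**The concern.** The sentence in 12c.i does not fit the data or the design.

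A Chi-squared test compares counts in categories. To apply it to a T-score, someone must first cut the score, and the SAP gives no cut-point. The result would also not supply the mean difference and interval that section 6 asks for.

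Schools were randomised, so children in one school, and their parents, may resemble each other. An ordinary Chi-squared test treats them as independent. Whenever scores cluster by school, its p values are too small.

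The SAP therefore names two between-arm tests for the same ten scores at two time points. An analyst who follows 12c.i literally would produce a second p value for each, from a method that does not hold its nominal error rate. Section 10 promises control of the false discovery rate but does not say which p values enter it. The primary outcomes are not affected.

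**Working it through.** **1. The sections side by side.**

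| SAP section | Scale implied | Method | Allows for schools? |
|---|---|---|---|
| 7b | Continuous T-score, mean 50, SD 10 | – | – |
| 12c.i | Categorical | Chi-squared test | No |
| 12c.iii | Continuous | Linear mixed model | Mixed model, but random effect not named |
| 6 | Continuous | Mean difference, 95% CI, p value | Not stated |

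Section 12c.i is out of line with the other three. Within the SAP no categorical secondary outcome remains to which its sentence could apply.

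**2. The SAP's own cluster figure.** No stated number is in dispute, but the section 4 power statement ("7 schools per study arm and an average of 50 students per school will provide 90% power") shows that the SAP plans for clustering. Its inputs are a difference of 4 hours, SD 8.0, ICC 0.05 and alpha 0.05.

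- Design effect = 1 + (50 − 1) × 0.05 = 3.45
- Effective number per arm = 7 × 50 / 3.45 = 101.4
- Standard error = 8 × √(2/101.4) = 1.123; noncentrality = 4/1.123 = 3.56
- Two-sided t test with 2 × (7 − 1) = 12 degrees of freedom: power 90.4%, which agrees with the stated 90%

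**3. What an unclustered Chi-squared test would do.** Inputs:

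- *ICC of the T-score:* assumed. Section 4 gives 0.05 for attendance and vaccination only. Range used here: 0.01 to 0.10.
- *Cut-point:* assumed at 50, the mean of the scale.
- *Children per school (m):* 50 from SAP section 4; 900/14 = 64.3 from the enrolment target; 290/7 = 41.4 from the roughly 290 intervention-arm parents with baseline data mentioned in the Protocol's Aim 3 enrolment criteria.

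Cutting a normal score at its mean lowers the ICC. The binary ICC is (2/π) × arcsin(ICC), so 0.05 becomes 0.032 and 0.01 becomes 0.0064.

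Design effect: DE = 1 + (m − 1) × binary ICC. Actual type I error of a nominal 5% test = 2 × [1 − Φ(1.96/√DE)].

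| m | DE (ICC 0.05) | Type I error | DE (ICC 0.01) | Type I error |
|---|---|---|---|---|
| 41.4 | 2.29 | 19.5% | 1.26 | 8.1% |
| 50 | 2.56 | 22.1% | 1.31 | 8.7% |
| 64.3 | 3.02 | 25.9% | 1.40 | 9.8% |

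**4. Check by simulation.** Null T-scores (mean 50, SD 10, 7 + 7 schools, 4,000 trials per scenario) were cut at 50 and compared by Chi-squared test. A t test on school means was run on the uncut scores.

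| ICC | Chi-squared, m = 50 | Chi-squared, m = 64 | t test on school means |
|---|---|---|---|
| 0.01 | 8.3% | 9.1% | 4.3% to 5.1% |
| 0.05 | 21.3% | 24.3% | 5.0% |
| 0.10 | 34.2% | 37.8% | 5.0% |

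The simulation agrees closely with the formula. A comparison that respects the schools holds about 5%.

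**The case against.** The strongest defence is that the sentence sits under a descriptive heading. The section devoted to secondary outcomes assigns the mixed model, in terms, to decide statistical significance, and section 6 asks for quantities that a Chi-squared test cannot give. Most of the SAP therefore points to one method. This stands in part. A reader might infer that the SAP leaves the choice of test open until the data are seen, and the documents do not support that. What remains is that 12c.i still names a between-arm significance test for these outcomes and nothing in the SAP withdraws it.

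A second defence is that the sentence was meant for a binary outcome, since the Protocol lists vaccination as secondary. That may explain where it came from. The SAP makes vaccination co-primary, however, and an unclustered Chi-squared test would be wrong for it too in a school-randomised trial.

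A third point concerns size. A reader might apply the design effect for the continuous score (1 + 63.3 × 0.05 = 4.16 at 64.3 per school) and quote a type I error of about 34%, or about 26% at 41.4 per school. Those figures describe an unclustered test on means. The Chi-squared test needs a cut score, whose ICC is smaller, so they overstate the error of the test actually named.

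**Conclusion.** The sentence in SAP 12c.i is wrong as written. It names a test that does not suit continuous T-scores, gives no cut-points, ignores school randomisation, and conflicts with SAP 12c.iii and section 6. This conclusion comes from the text alone and needs no number.

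The size is illustrative. With an assumed T-score ICC of 0.05 and an assumed cut at 50, the false-positive rate of a nominal 5% test is about 20% to 26% with 41 to 64 children per school, and about 22% at the SAP's planning size of 50. At ICC 0.01 it is about 8% to 10%. If T-scores did not cluster by school at all, there would be no inflation from this source, but the mismatch with the data type and the conflict between sections would remain.

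The defect is confined to secondary outcomes and should be corrected.

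**What to change.** 1. In SAP 12c.i, delete the part of the sentence that calls for comparison by Chi-squared tests, so that secondary outcomes are only summarised there.
2. In SAP 12c.iii, state that the linear mixed model is the only between-arm test of the secondary outcomes.
3. In the same section, add a school random effect. This is an addition: 12c.ii names school random effects for other outcomes, but 12c.iii names none.

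Separately, and optionally, adjust for the baseline T-score. Section 7b already has it collected, so no new data are needed. This may improve precision but is not part of the correction.

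The cost is a few words deleted and one or two sentences added to the SAP. Data collection, sample size and the primary analyses do not change.

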### *Inferential Analyses:*

To determine if absenteeism differs between participants given COVID-19 educational material and the participants in the control group, we will conduct a complete-case analysis to compare mean absences between the intervention and control groups using a two-sample t-test.

We hypothesis implementing three COVID-19 education comic books for children and two COVID-19 education videos for parents will lower child's absenteeism and COVID infection rates and increased vaccine uptake.

School days missed will be modelled by a mixed zero inflated negative binomial model, with school specific random effects to account for clustering. COVID positive testing results will be modelled by a mixed logistic regression model, with school specific random effects to account for clustering.

Vaccine uptake will also be analyzed by mixed logistic regression model.

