### Aim 2 Study Procedures:

Families will have three options to enroll children in the study: online through a website portal (Project REDCap), through a paper enrollment packet that will be distributed by our staff to students at school, or with assistance from study staff over the phone.

[figure not shown]
- Parents/guardians who choose to enroll children in the study online will provide informed consent by reading and e-signing consent and assent forms through a web-based REDCap portal, and then the participant's parent/legal guardian will complete a baseline enrollment questionnaire.
- The paper enrollment packet will include a flyer advertising the study, a guide for filling out the packets, consent and assent forms, and the enrollment questionnaire. Parents who prefer to enroll their child with the paper enrollment packets will fill out the enrollment packet and their child will return the completed packet to a secure lock box available at school. Study staff will pick up the consent enrollment packets from the lock box and enter the participant's information into REDCap. If there is information missing or issues with the paperwork, a staff member will call or email the parent of the participant to collect any missing information from their paper packet.
- Parents/guardians who choose to enroll with staff assistance over the phone will be verbally guided through the REDCap consent/assent forms and enrollment questionnaire.

Upon enrollment, randomization will occur per plan below:

**RCT Randomization Plan:** The randomization plan was developed by the study biostatistician. The schools will be matched in pairs with the primary match guided by the population of English Language Learners in the elementary schools and the secondary match on the size of the schools. The proportion of English Language Learners is highly correlated with low income and migrant status so will serve as a surrogate for all three characteristics. Size is moderately correlated to the proportion of English Language Learners. Once the study launches, each school within a pairing will be randomly assigned to either the Control or Intervention group.

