## 7. Outcome Definitions

### a. Primary Outcomes

The three co-primary outcomes for the trial are school absenteeism, COVID-19 testing, and COVID-19 vaccine uptake. Absenteeism are the student's school attendance data for 2022-2023 school year, COVID-19 data are captured through school testing and self-reported survey, and COVID-19 vaccine uptake data are captured through self-reported survey. All children and parent data after randomization will be included in the intention to treat analysis.

**Absenteeism:** total number of school days missed by each individual student participant, both for the entire school year and month-by-month, as captured and shared with us by school district administrative data systems. Absenteeism will also be measured by school days missed and will be a count variable.

**COVID-19 testing:** Health reports from the school are provided for the 2021-2022 and 2022-2023 school year that list positive covid test results of study participants with the date of testing and the school of attendance. Positive COVID test results will be a binary yes/no variable.

**COVID-19 vaccine uptake:** Parents are asked at enrollment to report their vaccination status and their child's vaccination status. At post survey 1 and post survey 2 the parent is asked to report if they or their child have received any COVID-19 vaccine or booster since enrollment. Vaccination status will be a binary yes/no variable.

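### Co-primary absenteeism has two competing tests: a student-level t-test that ignores school randomisation and a school-random-effect count model, with no rule for which decides

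*SAP*

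**What the plan says.** SAP section 7.a: "The three co-primary outcomes for the trial are school absenteeism, COVID-19 testing, and COVID-19 vaccine uptake". The same section defines absenteeism through days missed: "Absenteeism will also be measured by school days missed and will be a count variable".

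The unit of randomisation is the school. SAP section 3: "Schools are randomized 1:1 (matched by school size and English language learners) to either intervention or control group". The RCT Randomization Plan in Protocol section V adds that "each school within a pairing will be randomly assigned to either the Control or Intervention group".

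Under Inferential Analyses in SAP section 12.c.ii, two analyses of this outcome follow each other:

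- To answer whether absenteeism differs between the groups, "we will conduct a complete-case analysis to compare mean absences between the intervention and control groups using a two-sample t-test". No school term is mentioned.
- "School days missed will be modelled by a mixed zero inflated negative binomial model, with school specific random effects to account for clustering".

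Neither is labelled primary, supportive or descriptive. Three other places bear on the choice:

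- The opening paragraph of SAP section 12.c.ii (same text in Protocol section XI) does name a primary analysis. It is a linear mixed model of onsite learning hours per week, which is a different variable from days missed.
- SAP section 6 gives a reporting format for continuous outcomes, the primary outcome included ("together with the mean between-group difference, 95% confidence interval for the difference and p value"), and another for binary outcomes. It gives none for counts.
- SAP section 10 promises false discovery rate control without saying which p-values enter.

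**The concern.** A two-sample t-test on students takes its standard error from the variation between students. When whole schools are allocated, the arm difference also carries the variation between schools, and with seven schools per arm that part does not average out. The t-test's standard error is then too small, and chance differences between schools are declared an effect too often.

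The clustered count model would protect against this if it were the deciding analysis. The SAP does not say that it is. The t-test comes first, is the analysis tied directly to the question of whether absenteeism differs, and sits under inferential rather than descriptive analyses. Of the two analyses of days missed, it is also the only one that directly yields a mean difference with interval and p value.

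Two things are at stake: the false-positive rate if the t-test is the result relied on, and a choice between two possibly conflicting p-values made after both are known.

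**Working it through.** **Inputs from the documents.** 7 schools per arm; m = 50 students per school (SAP section 4), or 900/14 = 64.3 from the total enrolment target (SAP section 2); ICC 0.05 and type I error 0.05 (SAP section 4: "assuming intra-cluster correlation (ICC) of 0.05 and type I error rate of 0.05"); two-sided, from the caption of the table in the same section; 4 hours per week with SD 8.0 for the stated power.

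**Assumptions.** SAP section 4 gives ICC 0.05 for attendance hours and vaccination; here it is assumed for days missed. The share r of between-school variance removed by matching is not given, so a range is shown. School sizes are taken as equal.

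**Step 1. Reproduce the plan's own figure.** The design effect is 1 + (m − 1) × ICC = 1 + 49 × 0.05 = 3.45. The effective number per arm is 350/3.45 = 101.4. The noncentrality is 4 / (8 × √(2/101.4)) = 3.56. With 12 degrees of freedom (14 schools minus 2) the power is 90.4%, against the stated 90%. A normal approximation gives 94.5%. The sample size therefore rests on an analysis at school level with ICC 0.05.

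**Step 2. False-positive rate of the student-level t-test.**

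- True variance divided by the variance the t-test assumes: R = (1 − ICC) + (1 − r) × ICC × m. With r = 0 this is the design effect of step 1.
- Two-sided rate = 2 × [1 − Φ(1.96/√R)].

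With ICC 0.05:

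| r | R, m = 50 | Rate | R, m = 64.3 | Rate |
|---|---|---|---|---|
| 0 | 0.95 + 2.50 = 3.45 | 29.1% | 0.95 + 3.21 = 4.16 | 33.7% |
| 0.3 | 2.70 | 23.3% | 3.20 | 27.3% |
| 0.5 | 2.20 | 18.6% | 2.56 | 22.0% |
| 0.8 | 1.45 | 10.4% | 1.59 | 12.0% |

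**Step 3. Other ICCs, no matching gain.** ICC 0.01 gives 10.8% (m = 50) and 12.5% (m = 64.3); ICC 0.10 gives 42.0% and 46.9%. The SAP's detectable-difference table uses these two values, for classroom clusters. The mildest case examined (ICC 0.01, m = 50, r = 0.8) has R = 0.99 + 0.10 = 1.09 and a rate of about 6.0%.

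**Step 4. Simulation** (7 pairs, normal outcomes, 10,000 trials per setting).

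- At ICC 0.05 the t-test rejected in 29.8% (m = 50) and 33.4% (m = 64) of null trials with r = 0, and in 10.4% and 12.4% with r = 0.8.
- A paired t-test on the seven pairs of school means rejected in 4.7% to 5.4% across all 18 settings (ICC 0.01, 0.05, 0.10; r 0, 0.3, 0.8; m 50, 64).
- An unpaired t-test on the 14 school means rejected in 4.6% to 5.3% with r = 0, and was conservative (0.4% to 4.1%) when matching helped.
- With skewed counts (zero-inflated negative binomial, mean 10 days before zero inflation, 5% extra zeros, all assumed; realised ICC 0.044) the student-level t-test rejected in 27.6% (m = 50) and 32.1% (m = 64). The result does not depend on normality.

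**The case against.** The strongest reply is that the problem is already largely handled. A school-random-effect model for days missed stands in the same part of the SAP, attendance hours have a model with school and classroom random effects that is called primary, and the trial is sized with an ICC. On that reading the t-test is a simple unadjusted comparison and the models carry the inference. This is plausible, and it limits the defect to a missing rule. It does not supply the rule: no passage gives the t-test that lesser role, and descriptive analyses have their own section (12.c.i).

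The 29% to 34% figure is also conditional. It needs the t-test to decide, ICC 0.05 to hold for days missed, and matching to gain nothing. The last is the least favourable end of the range, because the protocol pairs schools on the proportion of English Language Learners, which it describes as closely related to income and migrant status, and then on size. Enrolment may also be smaller. Protocol section IV (Aim 3 criteria) mentions about 290 eligible intervention-arm parents, or 290/7 = 41.4 per school. As a rough proxy, that gives 25.9% with no matching gain and 9.3% with r = 0.8. These points move the size, but no case examined falls to 5%.

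Finally, the reporting format in SAP section 6 could refer to the continuous hours outcome, whose mixed model also yields a mean difference and interval. That is fair. Section 6 does not show that the t-test will be the reported result; it only fails to settle the matter for a count.

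**Conclusion.** The point holds and should be fixed. The SAP gives co-primary absenteeism two inferential analyses, one of which is invalid for a trial that randomised schools, and does not say which decides. If the t-test decides, its two-sided false-positive rate is 29.1% to 33.7% at ICC 0.05 with no matching gain, and 10.4% to 12.0% if matching removed 80% of between-school variance. Over all ICCs and matching gains examined at the planned cluster sizes it runs from about 6% to 47%. These figures rest on the SAP's ICC being carried over to days missed, on assumed matching gains, and on equal school sizes. They say nothing against the clustered count model, which is the reason the point is one of hierarchy and not a fatal flaw.

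**What to change.** In SAP section 12.c.ii, delete the student-level t-test or replace it with a school-level comparison, and name one cluster-adjusted analysis as decisive for absenteeism. Its p-value should be the one that enters the false discovery rate procedure.

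State small-sample inference that fits the chosen analysis:

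- paired comparison of the seven matched pairs: 6 df, critical t 2.447;
- unmatched comparison of 14 school means: 12 df, 2.179;
- school-level comparison with the two matching variables as covariates: 10 df, 2.228;
- if the zero-inflated negative binomial model decides, a p-value from re-randomising arm within pairs: 2^7 = 128 allocations, smallest two-sided p = 2/128 = 0.016.

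Add to SAP section 6 the effect measure and interval to be reported for a count outcome.

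A minor clean-up: remove the chi-squared comparison of secondary outcomes from SAP section 12.c.i. The SAP's secondary outcomes are T-scores, and section 12.c.iii already assigns them to linear mixed models.

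The cost is SAP wording, with no new data. Intervals for absenteeism will be wider than the t-test's. Pairing also costs degrees of freedom: with the step 1 inputs and no matching gain, 6 df gives 84.1% power at 50 students per school, against 90.4% with 12 df.
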